### **Introduction:**

The 1st cases of COVID-19 were reported by the Chinese officials to the WHO by 31 December 2019. Worldwide, the total cases by 23 April 2020 are 2,544,792 confirmed cases and 175,694 deaths [1]. No consensus on a certain drug therapy for COVID-19 infection. A lot of drugs are under trial or empirically included in treatment protocols for COVID-19. Drug re-purposing is the most widely used method for rapid response in the face of this epidemic. Trials to invent denovo medicines may not be the perfect rationale, while the death and infection toll is on the rise hourly.

One of these previously FDA approved drugs is Ivermectin. Ivermectin is FDA-approved drug for *Onchocerca volvulus* and

Lymphatic Filariasis [2]. It is known to have wide-spectrum antiviral activity against number of viruses under in vitro condition. [3-6] Ivermectin has been shown to inhibit the nuclear import of host and viral proteins. It has been demonstrated to limit infection by some RNA viruses including influenza, dengue and West Nile viruses. Ivermectin has similarly been shown to be effective against the DNA virus pseudorabies virus (PRV) both in vitro and in vivo. In an in vitro study, ivermectin was found to be an inhibitor of the SARS-CoV-2, with a single addition to Vero-hSLAM cells 2 h post infection with SARS-CoV-2 able to effect ~5000-fold reduction in viral RNA at 48 h. [7,8]

### **Rationale**

Previous studies demonstrated the antiviral role of Ivermectin and preliminary results from recent experimental reports highlighted an in vitro capability of withholding SARS-CoV-2 replication

### **Research question**

Is oral Ivermectin can prevent symptomatic COVI-19 infection in family close contacts with patients diagnosed as having the disease by RT-PCR

### **Hypothesis**

Ivermectin has an antiviral effect and may be effective in preventing development of symptomatic infection in family close contacts with patients having COVID-19

### **Aim**

To study oral Ivermectin as a prophylactic treatment in family close contacts with COVID-19 patients in the form of development of symptoms

### **Objectives**

To study the effect of oral Ivermectin as a prophylactic option in contacts with COVID-19 patients

### **Individuals:**

Adult family close contacts to COVID-19 positive patients diagnosed by RT-PCR.

### **Materials and Methods:**

**Study Design** interventional study

**Sample Size:** Family close contacts to 50 patients diagnosed as having COVID-19 by RT-PCR

**Location:** Isolation facilities/Zagazig University Hospitals

**Inclusion:** Age more than 16 years, Asymptomatic household close contacts

**Exclusion:** people previously treated for COVID-19, asymptomatic contacts with who have HRCT chest done and suggestive for COVID-19 infection

### **Intervention :**

All documented asymptomatic family contacts, starting on day of diagnosis of their index case will receive Ivermectin according to body weight as follows:

40-60 kg : 15 mg

60 -80 kg :18 mg

> 80 kg : 24 mg

This will be given as one dose at day one (diagnosis day), repeated once at day 3

In literature, individuals can receive 600mcg per Kg of ivermectin daily for 3 days without side effects (9,10)

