### **Follow up:**

1-These asymptomatic persons will be followed up for 2 weeks after the diagnosis of index case for:

Symptoms development,

Radiological evaluation if symptoms developed (HRCT chest)

Swabs for SARS-2 Virus if symptomatic

Recording possible side effects during treatment: eg sleepiness and fatigue

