## Consort Flow diagram of Ivermectin prophylaxis trial

## **Statistical analysis**

All data were collected, tabulated and statistically analyzed using SPSS 22.0 for windows (IBM Inc., Chicago, IL, USA) and MedCalc 13 for windows (MedCalc Software Bvba, Ostend, Belgium). Continuous Quantitative variables were expressed as the mean  $\pm$  SD & median (range), and categorical qualitative variables were expressed as absolute frequencies (number) & relative frequencies (percentage). Continuous data were checked for normality by using Shapiro Walk test. Mann-Whitney U test was used to compare between two groups of non-normally distributed data. Categorical data were compared using Chi-square test or Fisher's exact test when appropriate. Relative risk and its 95%Confidence interval (CI) was calculated to estimate risk of COVID-19 infection in addition forest plot was plotted. Univariate and multivariate binary logistic regression were built to find predictors for COVID-19 protection. All tests were two sided. p-value < 0.05 was considered statistically significant.

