## Results

As regard index cases, there were 9 (11.8%) mild , 44 (57.9%) moderate and 23 (30.3%) severe cases. In the ivermectin group, there were 8 (53.3%) mild , 6 (40%) moderate and 1 (6.7%) severe cases. While in the no-intervention group, there were 31 (52.5) mild, 21 (35.6%) moderate and 7 (11.9%) cases.

[figure not shown]

Figure (1): Scatter plot shows relationship between contact time in days and number of contacts that developed COVID-19; dashed line represent best fitted line (quadratic model).

There was insignificant linear correlation between contact time in days and number of contact that developed COVID-19. The appropriate forecasting for number of contact that developed COVID-19 based upon contact time in days was quadratic model.

[figure not shown]

Figure (2): Box plot shows relationship between isolation and number of contacts that developed COVID-19.

There was insignificant difference between index cases isolated at hospital and index cases isolated at home regarding number of contact that developed COVID-19 where mean number of contact that developed COVID-19 ( $\pm$ SD) was 2.14 ( $\pm$ 1.35) versus 2.07 ( $\pm$  2.26) respectively (p-value=0.280)

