**a: Chi-square test; b: Mann Whitney U test; p < 0.05 is significant.**

**Table (1)** shows that there was no significant difference between both arms as regard gender, age or comorbidities. The median (range) age for both groups was 38 (16-94) and 35 (16-78) years respectively.

The most common comorbidities were; hypertension in 16 (7.9%) and 13 (12.9%), DM in 13 (6.4%) and 10 (9.9%), bronchial asthma in 7 (3.4%) and 2 (2%), ischemic heart disease in 6 (3%) and 1 (1%), hypothyroidism in 5 (2.5%) and 1 (1%), chronic kidney disease in 2 (1%) and 1 (1%), liver

cirrhosis in 1 (0.5%) and 1 (1%), cardiomyopathy in 2 (1%) and 0% in both ivermectin and no-intervention group respectively.

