**a: Chi-square test; b: Mann Whitney U test; p< 0.05 is significant.**

**Table (2)** shows that 15 contacts (7.4%) developed COVID-19 in the ivermectin arm compared to 59 (58.4%) in the no-intervention arm, all of them were symptomatic, according to the study protocol . The difference was highly significant ( $p<0.001$ ). The median (range) days for developing the disease was 2 (2-6) in ivermectin group compared and 4 (2-10) in the no-intervention group, the difference was significant ( $p<0.017$ ). Ten contacts (66.6%) developed symptoms in 1st 3 days in ivermectin group, and none developed it after 6 days. In the no-intervention arm, 25 (42.3%) developed symptoms in the 1st 3 days and continued to the 10 days.

HRCT of the chest was performed in 14 out 15 contacts and in 58 of the 59 contacts who developed symptoms in ivermectin and no-intervention groups, respectively. The missed one case in each arm had symptoms and positive RT-PCR without other investigations. Chest HRCT was positive for

COVID-19 in 7 (50%) and 28 (48.3%) in ivermectin and no-intervention groups, respectively.

Complete blood count was performed also in 14 and 58 contacts who developed symptoms in ivermectin and no-intervention groups respectively. Positive criteria in CBC was present in 12 (85.7%) and 53 (91.4%) in ivermectin and no-intervention groups respectively.

**Table (3): Comparison between Ivermectin arm and non-intervention arm regarding protection rate stratified by basic characteristics.**

|                     |          | Protection rate |                      | Testa  | p-value |
|---------------------|----------|-----------------|----------------------|--------|---------|
|                     |          | Ivermectin arm  | Non-intervention arm |        |         |
| All patients        |          | 92.6%           | 41.6%                | -----  | -----   |
| Index case severity | Mild     | 92.9%           | 35%                  | 11.381 | 0.001   |
|                     | Moderate | 95.6%           | 55.8%                | 42.666 | <0.001  |
|                     | Severe   | 85.2%           | 28.9%                | 29.928 | <0.001  |
| Age                 | ≤60      | 93.8%           | 41.3%                | 91.514 | <0.001  |
|                     | >60      | 84%             | 44.4%                | 5.320  | 0.034   |
| Gender              | Male     | 94.3%           | 42%                  | 53.482 | <0.001  |

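### The written plan treats every contact, but the results compare 203 treated with 101 unexplained untreated contacts, and the quoted OR of 12.533 is not a between-arm comparison

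*Combined protocol and SAP*

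**What the plan says.** The planning sections describe one group.

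- **Intervention:** "All documented asymptomatic family contacts, starting on day of diagnosis of their index case will receive Ivermectin according to body weight".
- **Materials and Methods, Sample Size:** "Family close contacts to 50 patients diagnosed as having COVID-19 by RT-PCR". The design is given only as interventional; no comparator or allocation method is named.
- **Follow up:** "These asymptomatic persons will be followed up for 2 weeks after the diagnosis of index case", meaning the same treated contacts.

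Two groups first appear under Statistical analysis, in the past tense: "Mann-Whitney U test was used to compare between two groups of non-normally distributed data". That section also says "Univariate and multivariate binary logistic regression were built to find predictors for COVID-19 protection" and describes no allowance for contacts sharing a household.

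The Results are a two-arm comparison. For the index cases, "there were 9 (11.8%) mild , 44 (57.9%) moderate and 23 (30.3%) severe cases". Table (1) has 203 contacts in the ivermectin arm and 101 in the non-intervention arm, and the text below it "shows that there was no significant difference between both arms as regard gender, age or comorbidities". The text under Table (2) reports that "15 contacts (7.4%) developed COVID-19 in the ivermectin arm compared to 59 (58.4%) in the no-intervention arm". Table (4) prints a univariate OR for arm of 12.533 (7.408 to 21.205), with non-intervention as reference, and a multivariate OR of 11.445 (4.444 to 29.475). The closing text (which calls this Table (5)) presents both as comparisons with no intervention and words the result as a protective role of ivermectin.

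**The concern.** If every eligible contact was to be treated, the reader must know how 101 contacts came to be untreated. Refusal, a different time period, a different place and random allocation each give the difference a different meaning. Without that information the supplied text supports an association, and adjusting for measured covariates does not repair unknown selection.

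The univariate OR cited for the protection claim also does not follow from Table (2). An error running through the whole column would affect the list of predictors and the reader's view of what adjustment does to the arm effect.

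**Working it through.** **1. Plan against analysis.** Planned index cases: 50. Reported: 9 + 44 + 23 = 76, consistent with the printed percentages (9/76 = 11.8%, 44/76 = 57.9%, 23/76 = 30.3%). Contacts analysed: 203 + 101 = 304, of whom 101/304 = 33% were untreated.

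**2. The arm OR.** Table (2) gives protected/not protected as 188/15 (ivermectin) and 42/59 (non-intervention). The Pearson chi-square without continuity correction is 95.351, as printed, so the counts are secure.

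- Printed figure reproduced: 188/15 = 12.533; CI exp[ln(12.533) ± 1.96√(1/188 + 1/15)] = 7.408 to 21.206. The control arm does not enter.
- Between-arm OR: (188 × 59)/(15 × 42) = 17.61; SE of the log OR = √(1/188 + 1/15 + 1/42 + 1/59) = 0.336; CI 9.12 to 34.00.

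**3. The rest of the univariate column.** An integer search using both percentages and the chi-square in each Table (3) row gives one solution per row. Protected/total, ivermectin then control:

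- mild 13/14, 7/20; moderate 129/135, 24/43; severe 46/54, 11/38
- age ≤60 167/178, 38/92; age >60 21/25, 4/9
- male 100/106, 21/50; female 88/97, 21/51
- no comorbidity 149/156, 34/75; comorbidity 39/47, 8/26

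Pooling arms gives the odds within each category. Dividing by the reference odds gives the OR:

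| Row | Printed | Within-category odds | Reference odds | Correct OR (unclustered 95% CI) |
|---|---|---|---|---|
| Ivermectin | 12.533 | 188/15 | 42/59 | 17.61 (9.12–34.00) |
| Mild | 1.429 | 20/14 | 57/35 | 0.88 (0.39–1.96) |
| Moderate | 6.120 | 153/25 | 57/35 | 3.76 (2.07–6.82) |
| Age ≤60 | 3.154 | 205/65 | 25/9 | 1.14 (0.50–2.56), p=0.76 |
| Male | 3.457 | 121/35 | 109/39 | 1.24 (0.73–2.09), p=0.43 |
| No comorbidity | 3.812 | 183/48 | 47/26 | 2.11 (1.19–3.75), p=0.011 |

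The within-category odds reproduce all six printed estimates and their intervals to rounding, and the printed p of 0.306 for mild. A logistic model fitted without a constant would give this pattern.

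**4. Effect on reading the adjusted OR.** From 12.533 to 11.445 the apparent fall is 1 − 11.445/12.533 = 9%. From the crude 17.61 it is 1 − 11.445/17.61 = 35%. Adjusting for severity alone, from the rebuilt counts, gives 16.28 (logistic with constant) or 16.35 (Mantel-Haenszel). The rest of the fall would have to come from age, gender and comorbidity, which Table (1) reports as balanced (p=0.175, 0.656, 0.619). In 1,600 random joint arrangements matching the counts, the arm OR was 16.6–19.7 with a constant and 12.2–14.0 without; a directed search reached 7.1 with a constant. So 11.445 is not shown to be wrong, but it needs checking.

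**5. Severity and clustering (secondary).** Rebuilt mild/moderate/severe counts are 14/135/54 against 20/43/38; Table (1) omits them. The chi-square is 19.35 on 2 df. Index severity is constant within a household, so with a design effect of 304/76 = 4 (assumed), 19.35/4 = 4.84 and p=0.089.

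- Crude RR of infection (derived): (15/203)/(59/101) = 0.126 (0.076–0.212).
- Control risk standardised to the ivermectin arm's severity mix: (14×13/20 + 135×19/43 + 54×27/38)/203 = 0.528, so RR = 0.0739/0.528 = 0.140. Mantel-Haenszel RR: 0.150 (0.090–0.251, unclustered).
- Stratum RRs, mild to severe: 0.11, 0.10, 0.21.
- Interval for the crude OR of 17.61 with 4 contacts per household and whole households in one arm, design effect 1 + 3 × ICC: ICC 0.1, 8.31–37.29; 0.2, 7.66–40.48; 0.5, 6.22–49.84.

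**The case against.** The strongest reply is that the missing explanation may sit in material that was not available: a flow diagram is headed but not reproduced, and front pages were removed. That stands as a limit. It cannot be said that the full file is silent, only that the Intervention, Sample Size and Follow up sections do not describe the comparison analysed.

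Second, at 4 contacts per index case the 203 treated contacts correspond to 203/4 = 50.75 index cases, close to the planned 50. The planned households may all have been treated and a comparator added, so that 50 against 76 is the same deviation as the extra arm. This is plausible, but index cases are not split by arm, and an added comparator equally needs documenting.

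Third, the figure of 4 contacts per household is itself uncertain. The Results report a mean of 2.07 to 2.14 contacts developing COVID-19 per index case by place of isolation. Over 76 index cases that is about 157 to 163, against 15 + 59 = 74 in Table (2), although those means may cover only a subset. The design effects are therefore illustrative. At 2.5 instead of 4, the severity imbalance has p=0.021.

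Fourth, the printed multivariate interval is already wide: 29.475/4.444 = 6.6 between its limits, against 40.48/7.66 = 5.3 for the crude OR at ICC 0.2. How far clustering would change the adjusted interval is unknown.

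Finally, the Table (4) error understates the crude association. That is correct, and it is why the objection to the protection claim rests on the comparator and not on the size of the OR.

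**Conclusion.** The concern holds and must be fixed. The written plan has one treated group; the analysis has two arms, with 101 of 304 contacts (33%) untreated and 76 index cases against 50 planned. On the supplied text the result is an association, and bias from unknown entry into the untreated arm cannot be sized.

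The Table (4) error is certain for the arm row, which follows directly from Table (2). For the other five rows it rests on counts rebuilt from Table (3), each with a unique solution. The arm OR should read 17.61, two printed univariate predictors (age and gender) disappear, and mild against severe falls from 1.429 to 0.88.

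Index-case severity does not explain the result: the adjusted RRs of 0.140 and 0.150 lie inside the crude interval and all three strata agree in direction. Severity and clustering are secondary, and the clustered intervals depend on the assumed ICC and household size.

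**What to change.** 1. Leave the Sample Size, Intervention and Follow up text as written and add a dated amendment or deviation statement. It should say that a second, untreated group was analysed, how and when each household entered its group, whether households were kept together, and why 76 index cases are reported against 50 planned. If the flow diagram or another page gives the rule, cite it there.
2. Unless random allocation is documented, replace the protection wording after Table (4) with: *ivermectin was associated with fewer symptomatic infections in a non-randomised comparison*.
3. Recompute the whole univariate column of Table (4) against the stated reference categories, and correct the closing text (17.61 in place of 12.533). Confirm that the multivariate model included a constant; if it did not, refit it and restate 11.445.
4. Add index-case severity to Table (1). Report the severity-adjusted estimate, with its RR, using household-clustered robust standard errors.

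The cost is text edits, one corrected table column and one re-analysis of data already collected, which needs an index-case identifier for each contact. Age and gender stop being univariate predictors, intervals will probably widen, and the conclusion becomes an association unless random allocation can be shown.

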### **Follow up:**

1-These asymptomatic persons will be followed up for 2 weeks after the diagnosis of index case for:

Symptoms development,

Radiological evaluation if symptoms developed (HRCT chest)

Swabs for SARS-2 Virus if symptomatic

Recording possible side effects during treatment: eg sleepiness and fatigue

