**OR: Odds Ratio; 95%CI: 95%Confidence Interval.**

**Table (5)** shows that ivermectin have very highly significant role in the protection of SARS-CoV-2 infection. . It has an OR of 12.533 and 11.445 when compared to no intervention in both univariate and multivariate models, respectively. Ivermectin protection was not affected by gender or comorbidities in multivariate model.

As regard ivermectin side effects, they were reported in 11 (5.4%) contacts. These were; diarrhea (1.5%), nausea (1%), fatigue (1%), sleepiness (0.5%), abdominal pain (0.5%), heart burn (0.5%), tingling and numbness (0.5%) and lastly burning sensation (0.5%)

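### The 5.4% side-effect rate has no comparator, and no rule separates a side effect from the symptom endpoint (minor; cheap improvement)

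*Combined protocol and SAP*

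**What the plan says.** The Follow up section opens with "These asymptomatic persons will be followed up for 2 weeks after the diagnosis of index case for" four items: symptoms, HRCT if symptoms develop, swabs if symptomatic, and "Recording possible side effects during treatment: eg sleepiness and fatigue". The persons meant are those of the Intervention section, which begins "All documented asymptomatic family contacts, starting on day of diagnosis of their index case will receive Ivermectin" and sets the timing: "This will be given as one dose at day one (diagnosis day), repeated once at day 3". The protocol text describes no untreated arm; one appears only in the analysis and results.

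The Statistical analysis section names no safety comparison. The Results, in the text after Table 4, say: "As regard ivermectin side effects, they were reported in 11 (5.4%) contacts". They then list diarrhoea, nausea, fatigue, sleepiness, abdominal pain, heartburn, tingling and numbness, and burning sensation. No corresponding count is given for the non-intervention arm.

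On efficacy, the text under Table 2 reports that "15 contacts (7.4%) developed COVID-19 in the ivermectin arm compared to 59 (58.4%) in the no-intervention arm". The Aim and Follow up sections define the outcome simply as the development of symptoms. They give no symptom list and no rule for deciding whether a complaint is a symptom or a side effect.

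**The concern.** Two separate things are at stake.

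**Safety.** Diarrhoea, nausea, fatigue and abdominal pain also occur in people who take nothing. A rate collected and reported only in treated contacts mixes background complaints with any drug effect. For a drug given to asymptomatic people, the excess over background is the quantity of interest, and it cannot be estimated here.

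**Efficacy.** The endpoint is subjective, the comparator is no intervention, and no blinding is described. A tired contact who has taken ivermectin could be recorded as having a side effect, a symptom, or both. A tired untreated contact can be recorded only as having a symptom. The two labels also compete in the same days: the doses fall on days 1 and 3, and "Ten contacts (66.6%) developed symptoms in" the first 3 days in the ivermectin group. This leaves room for differential ascertainment in either direction: complaints kept out of the endpoint in the treated arm, or drug effects counted as endpoint symptoms in that arm.

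**Working it through.** **Inputs.** Arm sizes 203 and 101, and cases 15 and 59 (Table 2); 11 contacts with side effects, and percentages by type (Results, text after Table 4); dosing days 1 and 3 (Intervention).

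**1. Reproduce the reported rate.** 11/203 = 5.42%, which matches 5.4%. Over both arms it would be 11/304 = 3.6%. The denominator is therefore the ivermectin arm alone. The exact (Clopper-Pearson) 95% limits are the 2.5% point of Beta(11, 193) and the 97.5% point of Beta(12, 192): 2.7% to 9.5%.

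**2. Counts by type, back-calculated on 203.** 1.5% is 3 contacts (3/203 = 1.48%), 1% is 2 (0.99%) and 0.5% is 1 (0.49%). This gives diarrhoea 3, nausea 2, fatigue 2, and 1 each for the other five, 12 in all. Twelve complaints in 11 contacts fits one contact having two.

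**3. What the missing comparator does.** The control counts below are assumptions; the documents give none.

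| Assumed events in 101 untreated | Difference, percentage points (Newcombe 95% CI) | Fisher p |
|---|---|---|
| 0 | 5.4 (1.1 to 9.4) | 0.018 |
| 1 | 4.4 (-0.6 to 8.5) | 0.068 |
| 2 | 3.4 (-2.1 to 7.7) | 0.23 |
| 5 | 0.5 (-6.1 to 5.4) | 1.0 |

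The same 11 events are compatible with a clear excess or with none.

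**4. Reproduce the efficacy result.** The Pearson chi-square without continuity correction for 15/203 against 59/101 is 95.351, as in Table 2. The relative risk is RR = (a/203)/(59/101), with 95% CI exp(ln RR ± 1.96 × SE) and SE = √(1/a − 1/203 + 1/59 − 1/101). For a = 15, SE = 0.262 and RR = 0.126 (0.076 to 0.212).

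**5. Reclassify side effects as cases.** This assumes one complaint per reclassified contact where types are added, and none already among the 15.

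| Complaints counted as symptoms | Ivermectin cases | Risk | RR (95% CI) |
|---|---|---|---|
| None (as reported) | 15/203 | 7.4% | 0.13 (0.08 to 0.21) |
| Fatigue, sleepiness (+3) | 18/203 | 8.9% | 0.15 (0.09 to 0.24) |
| Diarrhoea, nausea, fatigue (+7) | 22/203 | 10.8% | 0.19 (0.12 to 0.28) |
| All 11 contacts | 26/203 | 12.8% | 0.22 (0.15 to 0.33) |

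Each row is an upper bound for its set of complaints: any contact with two complaints, or already a case, lowers the count. The intervals and p-values ignore household clustering.

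**The case against.** The strongest reply is that this is ordinary descriptive safety reporting in a prevention study. The Research question, Hypothesis, Aim and Objectives concern prevention only, and 5.4% is given with no test and no claim against background. A reader might infer that the trial fails its own safety question. The documents pose no such question, so that reading is not supported. What stands is narrower: the rate is presented as one of ivermectin side effects, and the data cannot support that attribution.

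A reader might also infer that complaints were taken out of the endpoint in the treated arm. Nothing shows this. No passage makes the two labels mutually exclusive, and the overlap between the 11 and the 15 is not stated. Cases were also worked up: HRCT and CBC were done in 14 of 15 and 58 of 59, and the remaining case in each arm had a positive RT-PCR. That reply carries weight but is not complete. HRCT was positive in only 7 of 14 and 28 of 58, swab results are not tabulated by arm, and the work-up is triggered by a complaint first being called a symptom.

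Two further readings go too far. Recording only on treatment days is one reading of the wording, but the item sits under a 2-week heading and its window is never given in days. That the untreated contacts had the same 2-week follow-up is an inference from the results, where onset runs to day 10; its length and method are not described.

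Finally, adding a control column would not by itself give attribution. With symptomatic COVID-19 in 58.4% against 7.4%, an overall 14-day difference in fatigue or nausea would mostly measure the disease and could make the drug appear to prevent adverse events. Power would also be low: about 45%, 25% and 13% to distinguish 5.4% from assumed backgrounds of 1%, 2% and 3%. This objection stands, and it shapes the fix.

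**Conclusion.** The point holds as a minor one. The 5.4% (2.7% to 9.5%) is an uncontrolled rate and cannot be attributed to ivermectin. No rule keeps the labelling of complaints the same in both arms, and no blinding is described, so differential ascertainment is possible. The documents do not show that it occurred.

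It would be wrong to conclude that mislabelled side effects explain the efficacy result. Counting every reported side effect as a case, with none already among the 15, takes the RR only from 0.13 to 0.22, and the upper confidence limit of 0.33 is still far below 1. Counting diarrhoea, nausea and fatigue alone gives at most 0.19 (0.12 to 0.28). Clustering would be expected to widen these intervals by an amount the documents do not allow one to compute. The contrast is reduced but not removed, and the main consequence is for how the safety figure is read.

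**What to change.** **From existing data.**
- Label 5.4% as an uncontrolled rate, and state the recording window in days and how complaints were attributed.
- State how many of the 11 are among the 15 cases.
- Add a sensitivity analysis that counts treated contacts with overlapping complaints as symptomatic, naming the complaints included.

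**For further contacts or a repeat study.**
- Record the same complaints with one checklist, at the same contact times and over the same stated window in both arms.
- Apply one case definition that ignores arm and presumed cause.
- Report complaints by arm for the dosing window and for the full follow-up, separately for contacts who did and did not become COVID-19 cases. Splitting by case status is descriptive, since it conditions on an outcome, but without it the difference would mainly reflect COVID-19 symptoms.

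**Cost.** Slightly more data entry for the untreated contacts, provided they are followed on a comparable schedule, and a slightly less favourable RR in the sensitivity analysis. This is a cheap improvement.
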